We propose a randomized controlled design for this pilot 12-week trial of the behavioral intervention MET compared to KK+KY for improving cognitive performance and health in women at high risk of AD. We hope to control for nonspecific factors by using a gold standard active control condition that has demonstrated acceptability in this population.

The proposed study will to test whether KK+KY is superior to MET for improving cognitive functioning, health (including cardiovascular factors), and mood in women with high AD risk. All participants will be recruited from the UCLA Women's Cardiovascular Center, UCLA outpatient clinics and the UCLA Longevity Center Program. All participants will be identified as having high AD risk including subjective memory complaints and high cardiovascular risk based on the 2013 ACC/AHA Guideline on the Assessment of Cardiovascular Risk (Goff et al., 2014). Follow up of all enrolled subjects at 6- and 12-months (52 weeks total) will allow detection of any continued cognitive or health benefits.

b) Methods for reducing risk of bias:

Participants will be informed prior to enrollment that they will receive one of two evidence-based interventions for improving memory. Descriptions of the study will be designed to minimize risk of possible between group differences resulting from differences in treatment expectancy. Differences in treatment expectancy/ credibility will be tested for at baseline, week 12, and week 24 as specified below. We will also control for the "instructor" effect if several instructors teach classes. The feasibility of weekly yoga/MET classes and homework time was assessed during previous studies and found reasonable for participants to complete (Eyre et al., 2016; H. Yang et al., 2016). Behavioral raters will be blind to group assignment.

1. Study Population: We anticipate screening about 250 subjects to recruit 100 women with subjective memory complaints and high cardiovascular risk based on the 2013 ACC/AHA Guideline on the Assessment of Cardiovascular Risk. Participants will be recruited from the women's clinics and geriatric clinics at UCLA as well as the UCLA Longevity Center.

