Autonomic nervous system (ANS) and respiratory measures. In order to link genotype and neuroimaging data with respiratory and ANS functioning, we will perform a series of five tests: 1) rest; 2) paced breathing; 3) breath hold; 4) Valsalva maneuver; 5) hand grip. These tasks will provide detailed information about cardiorespiratory functioning. Continuous blood pressure will be assessed using a probe attached to two fingers of the same hand. An additional finger probe will be used to measure the Galvanic skin response (GSR) and chest electrodes will be applied for the electrocardiogram (ECG) and on the hand for an electromyogram (EMG). A respiratory belt around the patient's chest will provide breath rate data and a small probe attached to the cheek will measure changes in face skin temperature. End-tidal CO2 will be measured using a capnometer and spirometry will be used to investigate pulmonary capacity. Verbal instructions will be provided and a computerized task will indicate to the subjects when to begin and end each challenge, for example when to prepare for the breath hold (deep inhale followed by deep exhale and then hold at the top of the next deep inhale). Data will be recorded and time-locked using a BioPac system and associated software, which will also be used to process the data.

Randomization and treatment schedule:

After all screening and baseline test results are reviewed and eligibility criteria are confirmed, patients will sign the informed consent form. Next, participants will be randomized to either MET or KK+KY groups using a computer-generated random assignment scheme, which assigns participants in a 1:1 ratio to each group using a customized module built into the centralized data system. All behavioral raters will be blind to the group assignment, and participants will be asked not to disclose their group assignment to the raters.

Study intervention procedures:

Participants will be randomized to: (1) MET class for 60 minutes per week plus daily homework; or (2) KY class for 60 minutes per week plus daily KK homework. Participants will complete a questionnaire about their treatment expectations after their second class. Follow-up assessments immediately after the intervention (12 weeks) as well as at 24 and 48 weeks will test the effect of the interventions at both short- and long-term follow-up.

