Memory Enhancement Training Intervention. Patients will be informed that MET teaches specific memory strategies and has been shown to improve memory in adults with mild cognitive impairment. The standard detailed protocol for MET program is based on evidence based techniques that use verbal and visual association strategies and practical strategies for memory compensation (Gross et al., 2012; Verhaeghen et al., 1992). The MET program is manualized and includes components adapted from other effective memory training programs (Verhaeghen et al., 1992) such as: (1) Education about memory; (2) Preliminary instruction in the basic elements of memory strategies (i.e. "pre-training"); (3) Instruction in specific memory strategies; (4) Home practice with logs to track activity; (5) Addressing non-cognitive factors such as self-confidence, anxiety, and negative expectations; (6) Small (i.e. 10 persons) groups and short (60 min) sessions. The curriculum is divided into 12 weekly sessions which are organized in the same way in which trainers: (1) Document attendance, collect homework completion logs and assess engagement in alternative treatments; (2) Review the previous session's homework in order to reinforce home practice; (3) teach new techniques, reviews, and conduct in-class exercises, (4) assign homework for the upcoming week. Overall, in each session, roughly 15 minutes are devoted to reviewing the homework and 45 minutes is devoted to learning and practicing techniques. Specific techniques include: Visual associative learning strategies for learning faces and names (adapted from McCarty, 1980)(McCarty, 1980), verbal associative techniques such as the use of stories to remember lists: organizational strategies (categorizing items on a grocery list); forming good memory habits to recall where one places items, what one has done in the recent past (e.g. locking doors, turning off appliances); and how to remember future tasks (i.e., appointments). [name], a postdoctoral fellow supervised by [name], or a masters-level trainee supervised by [name] will teach the MET intervention.

KK+KY intervention:

Kundalini yoga (KY) class will be scheduled for 60 minutes weekly and will be conducted by a certified yoga teacher. The content and structure of the class will be similar across weeks: 1) Tuning in (5 minutes); 2) Warm up (10 minutes); 3) Pranayam (10 minutes); 3) Kriya (20 minutes); 4) Meditation (12 minutes) 5) Shavasana (3 minutes).

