Data will be analyzed using the SAS (v9.4) statistical package. Data will be examined initially to identify issues such as departures from normality, which might suggest the need for transformation (e.g., logarithmic). Demographic variables (e.g., age, gender, etc.) will be compared by treatment group and examined in relation to outcome variables; this would define one possible set of appropriate covariates, if needed. Correlations (a) among outcome measures and (b) among potential covariates will be examined to eliminate redundancy via possible data reduction, e.g., formation of composite scores or selection of single measures from sets of highly inter-correlated variables. Cognitive domain scores will be obtained as follows: for each neuropsychological test, raw scores will be converted to standardized (Z) scores with a mean of 0 and a SD of 1, based on all participants combined. Then, for each of the tests in a cognitive domain, the Z scores will be averaged to create a single Z score per cognitive domain.

The independent samples *t*-test or Chi-square test will be used to compare the demographic characteristics between the MET and KK+KY control group. The effect of intervention over time on the cognitive functions will be investigated in intention-to-treat (ITT) analyses. Measurements will be analyzed using linear mixed models; analyses will assume missing at random with missingness allowed. All models will include random intercepts to account for correlations between the repeated measures for each participant. The fixed components of the models will include effects of group and time and a group X time interaction, with post hoc analyses between times and groups. All statistical significance tests will be two-sided, and an alpha-level of 0.05 will be considered statistically significant for primary analyses and Bonferroni correction will be employed for post hoc analyses.

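### Both arms are taught in weekly classes, but neither the mixed model nor the power calculation allows for correlation within a class; between-arm standard errors are too small if the class ICC exceeds zero

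*Combined protocol and SAP*

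**What the plan says.** **Delivery.** Under Study intervention procedures, participants get either a weekly 60-minute MET class with daily homework or a "KY class for 60 minutes per week plus daily KK homework". The MET description lists "Small (i.e. 10 persons) groups and short (60 min) sessions" among its components, and its teachers may be a postdoctoral fellow "or a masters-level trainee supervised by" a senior colleague. The KK+KY intervention paragraph says the yoga class "will be scheduled for 60 minutes weekly and will be conducted by a certified yoga teacher"; it gives no class size.

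**Model.** The Data analysis section states: "All models will include random intercepts to account for correlations between the repeated measures for each participant". It continues: "The fixed components of the models will include effects of group and time and a group X time interaction". It lists no term for class, cohort or instructor.

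**Instructor.** In Study Design, under the methods for reducing risk of bias, the protocol says: "We will also control for the 'instructor' effect if several instructors teach classes". Neither the Data analysis section nor the Primary outcome paragraph repeats this or says how it will be done.

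**Power.** The Power analysis paragraph gives 45 completers per group, 80% power for equivalence within 0.62 at a true difference of zero, and 80% power to detect an effect of 0.60 on executive functioning. It mentions no ICC and no design effect.

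**The concern.** Women in the same class share a teacher, classmates and a calendar period. Their post-treatment scores may therefore be more alike than those of women in different classes of the same arm. The specified model allows for correlation within a woman over time but sets correlation between classmates to zero, and gives no reason for doing so.

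If the class variance is positive, the standard error of the KK+KY versus MET difference is understated. A superiority test, such as the one for executive functioning, then rejects too often. For an equivalence conclusion the error runs in the convenient direction: a confidence interval that is too narrow fits inside the margin more easily. The planned 45 per arm would also carry less information than the power paragraph assumes.

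**Working it through.** **Inputs from the documents:** 45 completers per arm; margin 0.62 (taken as SD units); true difference 0; secondary effect size 0.60; MET groups of about 10.

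**Assumptions:** SD 1; m = 9 or 10 completers per class in both arms (50 women in classes of 10 is 5 classes, or 9 completers each after 10% attrition); ICC 0.01, 0.02 or 0.05.

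**1. The plan's own figures.** With independent women, SE = √(2/45) = 0.2108.
- Equivalence by two one-sided tests at 0.05 each: power = 2Φ(0.62/0.2108 − 1.645) − 1 = 0.805. With 0.025 per side it would be 0.673, so 0.05 per side was evidently used.
- Secondary outcome: Φ(0.60/0.2108 − 1.960) = 0.812.

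Both reproduce the stated 80% with no design effect.

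**2. With class correlation.** Design effect DE = 1 + (m − 1) × ICC, and the true SE is √DE times the unclustered SE.
- Type I error of the unadjusted two-sided test = 2[1 − Φ(1.960/√DE)].
- False equivalence when the true difference lies at the margin = 1 − Φ(1.645/√DE).
- Power with clustering modelled uses SE = √(2 × DE/45) in the formulas of step 1.

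| ICC | DE (m = 9; 10) | Two-sided type I error | False equivalence (nominal 5%) | Equivalence power | Secondary power |
|---|---|---|---|---|---|
| 0 | 1 | 5.0% | 5.0% | 80.5% | 81.2% |
| 0.01 | 1.08; 1.09 | 5.9%; 6.0% | 5.7%; 5.8% | 76.4%; 75.9% | 78.2%; 77.8% |
| 0.02 | 1.16; 1.18 | 6.9%; 7.1% | 6.3%; 6.5% | 72.2%; 71.2% | 75.3%; 74.5% |
| 0.05 | 1.40; 1.45 | 9.8%; 10.4% | 8.2%; 8.6% | 59.9%; 57.5% | 67.2%; 65.7% |

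**3. If only MET is clustered.** The design effect averages to (1 + DE)/2. At m = 10 and ICC 0.01, 0.02 or 0.05 this is 1.045, 1.09 or 1.225. Type I error is then 5.5%, 6.0% or 7.7%, and equivalence power 78%, 76% or 69%.

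**4. Degrees of freedom, kept separate.** Five classes per arm leave 2 × (5 − 1) = 8 class-level df in the worst case. A t reference with 8 df lowers equivalence power to about 70% even at ICC 0. With m = 9 and ICC 0.01, 0.02 or 0.05 it is 65%, 61% or 48%. Much of that fall is loss of df, not clustering.

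**5. Which class term works.** The plan's treatment contrast is group by time. Assume pre/post data, five classes of 9 per arm, residual variance 0.4 per visit, and class variance 0.05 that arises only after classes start. A woman's change score has residual variance 2 × 0.4 = 0.8, and her own intercept cancels.
- SE without a class term: √(2 × 0.8/45) = 0.189.
- SE with a class intercept constant over time: still 0.189, because that intercept cancels from change as well.
- True SE: √[2 × (0.8/45 + 0.05/5)] = 0.236, which a class-by-time or post-baseline class effect recovers.

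**The case against.** **The instructor effect is already to be controlled.** This stands in part, so a reader who infers that shared teaching is ignored altogether goes too far. But the commitment applies only if several instructors teach, has no stated form, is missing from the Data analysis section, and does not cover different classes under one instructor. If each instructor teaches only one arm, which the intervention descriptions suggest but do not state, a fixed instructor effect cannot be separated from arm.

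**The ICC may be close to zero.** This is fair. The MET curriculum is manualized, home meditation follows standardized recordings, practice is individual and daily, and remote participation has been offered since March 2020. At ICC 0 the planned standard errors are valid. A reader might infer that the planned intervals are certainly too narrow; the documents give no ICC, so they do not support that.

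**Small classes are documented only for MET.** Correct. It is tempting to read both arms as groups of 10, but yoga class size is not given. The inflation is smaller if only MET is clustered.

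**The Data analysis section contains no equivalence test.** Also correct. Equivalence appears only in the Power analysis paragraph, so the false-equivalence rates apply only if equivalence is tested as that paragraph implies.

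**Ten classes estimate a class variance poorly.** True. In simulation at ICC 0.01 to 0.05 the ANOVA estimate is zero or negative in about 29% to 49% of trials. That is a reason for small-sample degrees of freedom; it does not justify fixing the variance at zero without comment.

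**Conclusion.** The omission is documented: delivery is by class in both arms, the model has a participant intercept only, and the power calculation treats 45 women per arm as independent. Its effect is conditional on a class ICC above zero.

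Under the assumptions above, with ICC 0.01 to 0.05, two-sided type I error is about 6% to 10% and equivalence power about 76% down to 57-60%. If equivalence is tested as implied, the false-equivalence rate is about 5.7% to 8.6%.

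A reader might infer from the 8-df figures that class correlation alone takes power below 50%. It does not: 8 df already give about 70% at ICC 0, and 8 df are the worst case. The point should be corrected before analysis. It does not by itself invalidate the trial.

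**What to change.** - Record class and instructor identifiers for every participant in both arms, and state the yoga class size.
- Add to the Data analysis section a random effect for class within arm that acts on post-baseline outcomes (class by time), with Kenward-Roger degrees of freedom. Do not rely on a class intercept that is constant over time.
- Carry the instructor commitment from the Study Design section into the Data analysis section and give its form.
- Restate the power for the primary and secondary outcomes over an assumed ICC range of 0.01 to 0.05, showing the effect of degrees of freedom separately.

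The cost is two data fields, one model term and a revised power paragraph, with no change to visits or classes. The downsides are wider intervals, less favourable stated power, and a class variance that about 10 classes estimate imprecisely.

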Behavioral regulation/ impulsivity will be assessed via an abbreviated (9-item) version of the Monetary Choice Questionnaire developed by Kirby and Marakovic (Kirby & Maraković, 1995). Because yoga is proposed to increase self-regulation, we expect that the yoga group will improve on this measure to a greater extent than the MET group. A recent study found that older adults with MCI showed significantly greater delay discounting than healthy controls at the small reward magnitude, leading the authors to propose delay discounting as a candidate marker for early dementia (Lindbergh, Puente, Gray, Mackillop, & Miller, 2014). Because these results were only significant at the small reward magnitudes, we are only using the small reward magnitude items (i.e., items for which the delayed reward is less than or equal to \$35).

Measures of medical comorbidity. Comprehensive assessment of vascular and nonvascular medical burden will be provided using screening ECG and medical assessments and the review of medical documentation and will include the Stroke Risk Factor Prediction Chart (SRF)(Ho et al., 1993; Truelsen et al., 1994) of the American Heart Association for rating cerebrovascular risk factors (5 min). This scale incorporates eight independent measures; age, presence and treatment of hypertension, diabetes, smoking, coronary vascular disease, atrial fibrillation and left ventricular hypertrophy and provides a score indicating overall risk for cerebrovascular disease and stroke. The Cumulative Illness Rating Scale-Geriatric (CIRS-G)(Salvi et al., 2008) is used for rating the severity of chronic medical illness and burden in 14 organ-systems (15 min).

Family History of Dementia. Because family history of dementia is a known risk factor, this will be assessed in the form of a yes/ no question during the in-person screening. This variable will be added as a covariate and investigated as a possible moderator of treatment effects.

Physical Activity and Meditation Practice. Degree of physical activity and meditation practice will be assessed and used as covariates in analyses of treatment effects. For physical activity assessment, we will be using the short International Physical Activity Questionnaire modified for the elderly (IPAQ-E) (Hurtig-Wennlöf, Hagströmer, & Olsson, 2010).

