Primary outcome: The analyses for the memory domain Z scores will use general linear mixed model (GLMM) analysis (e.g., SAS PROC MIXED). The two treatment groups will be compared for time course of cognitive domain z scores the initial endpoint EOT at 12 weeks and 6- and 12-months. Covariates may be included in the model as noted above. As noted above, the primary cognitive domain of interest for this proposal is memory. A separate GLMM as above will be estimated using memory domain z-scores as dependent variables. Executive Function will be examined as secondary outcome measure. Supplementary analyses of the follow-up period will look at the cognitive domain scores by treatment group controlling for values at EOT (post-treatment changes). Objective memory measures will be examined using a similar GLMM.

Exploratory Hypotheses: GLMM models as described above will be used to examine telomerase activity (overall level and TL) and inflammatory measures separately. Relationships between changes in markers of inflammation and telomerase activity to changes in cognitive scores, cognitive domain scores and fMRI measures will be examined using regression models within each group. Transformations of the measures will be performed as necessary.

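### Covariates may be chosen from baseline tests and outcome relations in the trial's own data, and this is not reconciled with the covariates named elsewhere; one baseline set should be fixed before unblinding

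*Combined protocol and SAP*

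**What the plan says.** Three parts of the combined document bear on covariates.

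- **Data analysis.** Demographic variables "will be compared by treatment group and examined in relation to outcome variables"; the text adds that "this would define one possible set of appropriate covariates, if needed". The comparison between arms is a significance test: "The independent samples *t*-test or Chi-square test will be used to compare the demographic characteristics". The core of the mixed model is fixed: "The fixed components of the models will include effects of group and time and a group X time interaction", with a random intercept per participant.
- **Primary outcome.** The option is carried into the model for memory: "Covariates may be included in the model as noted above". The comparison of interest is described this way: "The two treatment groups will be compared for time course of cognitive domain z scores".
- **Measures and Outcomes.** Of family history of dementia it says: "This variable will be added as a covariate and investigated as a possible moderator of treatment effects". The next paragraph commits in the same firm way to adjusting for physical activity and meditation practice.

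The document gives no candidate list, no threshold, no statement of whether arms are masked when the choice is made, and no date by which it is fixed. Gender is offered as an example of a demographic variable although only women are enrolled, so the candidates cannot be read off the text.

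**The concern.** With 1:1 randomisation any baseline difference between arms is chance. A test of it says nothing about whether a covariate is worth adjusting for; that depends on how strongly the covariate predicts the outcome. Looking at outcome relations in the trial's own data does address this, but it opens the choice of model to someone who can already see results.

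Two things are at stake. If the imbalance screen is applied mechanically, prognostic covariates are usually left out and precision is lost. If the optional wording is used freely, several models can be fitted and the most favourable one reported.

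The document also disagrees with itself. Three covariates are definite in one section, and covariates are optional in another. Two of the three, physical activity and meditation practice, are measured at screening and again at weeks 12, 24 and 48 (Table 4), with no statement that only the first value is used. One arm is a meditation intervention, so adjusting for later meditation practice could remove part of its effect.

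**Working it through.** **The plan's own figures.** From the Power analysis: 45 completers per arm, equivalence margin 0.62 (taken as SD units), true difference zero, 80% power. For two one-sided tests at 0.05 each, n per arm = 2 × ((1.645 + 1.282)/0.62)² = 44.6, rounded to 45, which reproduces. For executive function, effect 0.60 SD: n = 2 × ((1.960 + 0.842)/0.60)² = 43.6, rounded to 44; 45 per arm gives 80.4% by the t distribution, which also reproduces. Neither figure depends on covariates.

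**Single-visit comparison of arms, no true difference.** Inputs from the document: 45 per arm, two-sided 0.05. Assumed, because the document is silent: 2, 4 or 8 candidates, joint R² with the outcome of 0.1 to 0.5, screening at 5%. There were 8,000 to 10,000 simulated trials per setting, Monte Carlo standard error about 0.2 points. Entries are rejection rates in percent.

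| Candidates, R² | Fixed set | Imbalance screen | Outcome screen | Both required | Best of six rule-based models | Best of all subsets |
|---|---|---|---|---|---|---|
| 2, 0.1 | 4.8 | 4.8 | 4.9 | 4.8 | 6.7 | 7.2 |
| 2, 0.3 | 5.2 | 4.3 | 5.1 | 4.3 | 7.7 | 9.3 |
| 2, 0.5 | 5.3 | 3.6 | 5.3 | 3.6 | 8.4 | 11.0 |
| 4, 0.1 | 4.5 | 4.6 | 4.8 | 4.6 | 7.0 | 8.6 |
| 4, 0.3 | 4.8 | 4.2 | 4.7 | 4.3 | 7.9 | 12.4 |
| 4, 0.5 | 5.1 | 3.5 | 5.1 | 3.5 | 8.4 | 16.1 |
| 8, 0.3 | 5.0 | 4.0 | 4.9 | 4.1 | 9.1 | not run |

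The six rule-based models are unadjusted, all candidates, imbalance, outcome, both, and either. The screens taken one at a time are conservative or near nominal. Inflation appears only in the last two columns, where the best result is kept.

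**The planned group by time contrast.** Sixty simulated trials per setting were fitted with the random-intercept model, with and without covariates. With complete data, demographic main effects changed the group by time estimate by less than 1e-14 and its standard error by less than 0.001%. With dropout like that planned, the estimate moved by about 0.07 of a standard error on average, or about 0.11 with covariate by time terms. The group term moved by about 0.5 to 0.6 of a standard error, and its standard error fell by about 21%.

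A menu of nine models (unadjusted, imbalance-selected, six single covariates, full; each covariate correlated 0.3 with the outcome) was then tried in the mixed model, with 50 per arm, four visits, an assumed intraclass correlation of 0.65 and 1,500 runs (Monte Carlo standard error about 0.6 points):

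- Complete data: 5.1% for the best model, 5.1% unadjusted.
- 10% dropout per interval: 6.8% for the best model, 5.8% unadjusted.

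**What planned adjustment would gain.** At 0.60 SD with four fixed covariates and R² 0.3, power at a single visit is 91%, against 81% unadjusted, 82% under the imbalance screen and 81% when both conditions are required.

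For the baseline outcome, let ρ be the assumed correlation between baseline and follow-up. A change contrast has variance 2(1 − ρ) and a baseline-adjusted contrast has 1 − ρ². For a 0.5 SD effect, the noncentrality is 0.5/(SD × √(2/45)):

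- ρ = 0.5: SD 1.00 against 0.87, noncentrality 2.37 against 2.74, power about 65% against 77%.
- ρ = 0.8: SD 0.63 against 0.60, noncentrality 3.75 against 3.95, power about 96% against 97%.

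**The case against.** The strongest reply is that a reader might infer from the wording that the primary test itself is badly miscalibrated. With six candidates each correlated 0.3 with the outcome, keeping the best of those nine models in an ordinary regression at one visit gives 13% to 14%. The documents do not support carrying that figure to the primary analysis, for three reasons.

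- The planned model compares time courses. Time-fixed covariates cancel from that contrast with complete data and barely move it with dropout; the same menu of models adds only about 0 to 1 point.
- The Power analysis treats the primary aim as equivalence. Zero difference is then the state the trial hopes to demonstrate, so a rejection rate at zero difference is not the type I error of that claim.
- Followed as a strict imbalance screen, the text gives a conservative test, not a liberal one. The inflation comes from discretion over which model to report.

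It would also be wrong to say that every covariate is picked by testing, since three are named in advance. The Power analysis further promises to report all proposed analyses, which limits selective reporting, and post hoc comparisons are Bonferroni-corrected.

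All of this stands, but it does not remove the point. The promise to report everything does not say which covariate set is primary. Bonferroni counts comparisons, not models tried. The plan also includes post hoc comparisons between arms and follow-up analyses controlling for the end-of-treatment value, and it does not exclude covariate by time terms or time-varying covariates. Those are where free choice matters.

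**Conclusion.** The concern holds in a limited form. The text permits covariates to be selected by an uninformative test and by inspection of outcome data, leaves their use optional, and conflicts with the three covariates named under Measures and Outcomes.

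For single-visit superiority comparisons between arms, strict imbalance screening gives about 3.5% to 4.8% at nominal 5% and forgoes roughly 9 points of power in the setting examined (91% less 82%). Free choice of model gives roughly 7% to 16%. These ranges rest on assumed numbers and strengths of covariates, which the document does not supply. For the group by time contrast the effect is about 0 to 1 point under the dropout and correlation assumed. No rate is claimed for the equivalence aim, and the stated sample size is unaffected.

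**What to change.** Delete the use of between-arm baseline tests and outcome correlations as the means of choosing covariates; the baseline table can remain descriptive. Before unblinding, name one covariate set for the primary and secondary models, reconciled with the Measures and Outcomes section and using pre-randomisation values only. An example is age, years of education and family history of dementia, with physical activity and meditation practice at their screening values.

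Handle the baseline value of the outcome in one of two ways: as a covariate with only post-baseline visits as the response, or as a response in a mixed model that constrains the arms to a common baseline mean. It should not be both covariate and response. Report the unadjusted model and any other covariate set as sensitivity analyses.

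The example variables need no new data collection: family history, activity and meditation practice are in the assessment schedule, and age and education are already needed for the MMSE norms. The cost is a few degrees of freedom, a revised analysis section and a small re-specification of the mixed model.

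### Baseline memory is not prespecified as an adjustment in the primary model, so the between-arm contrast is likely less precise than the trial's own data allow

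*Combined protocol and SAP*

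**What the plan says.** The Data analysis section sets one model form for all cognitive outcomes. On the covariance it states "All models will include random intercepts to account for correlations between the repeated measures for each participant", and on the mean it states "The fixed components of the models will include effects of group and time and a group X time interaction". Tests are two-sided at 0.05.

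The Primary outcome paragraph applies this to the memory domain Z score and adds "Covariates may be included in the model as noted above". What is noted above is a comparison of demographic variables, of which the plan says "this would define one possible set of appropriate covariates, if needed". Two other covariates are named under Measures and Outcomes. On family history of dementia: "This variable will be added as a covariate and investigated as a possible moderator of treatment effects". On activity: "Degree of physical activity and meditation practice will be assessed and used as covariates in analyses of treatment effects". The baseline memory score is not named anywhere as a covariate. The only adjustment for an earlier outcome value is in the supplementary follow-up analysis, which controls for the end-of-treatment score.

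The plan does not list the levels of time. Hypothesis 1 is about improvement from baseline to week 12 within each arm, which implies that baseline is one level. The Primary outcome paragraph, however, describes the arm comparison as covering the "time course of cognitive domain z scores the initial endpoint EOT at 12 weeks and 6- and 12-months", without naming baseline.

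**The concern.** Baseline memory is scheduled for every woman before randomisation and is likely to be the strongest single predictor of the week-12 score. A model with free group, time and interaction terms lets the two randomised arms have different true baseline means. It then measures the treatment effect as a difference in change. This fixes the baseline slope at 1, where the best slope under equal SDs is r. The cost is a wider interval for the between-arm contrast on memory and on executive function, and chance baseline differences are over-corrected. Because the covariates are optional and their choice depends on the data, the decision to adjust is also left open until results can be seen.

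**Working it through.** **Inputs.** From Power analysis: 45 completers per arm, margin 0.62, true difference 0, 80% power. From Recruitment: about 10% dropout by week 12 and 35–36 per arm at 12 months. No correlation r is given, so it is assumed and varied from 0.3 to 0.9. SDs are first taken as equal at both visits.

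**1. The plan's own figure.** Two one-sided tests at 0.05 each, SD 1, normal approximation: SE = √(2/45) = 0.2108; 0.62/0.2108 = 2.941; 2.941 − 1.645 = 1.296; power = 2Φ(1.296) − 1 = 80.5%. The stated 80% reproduces.

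**2. Variance of the week-12 contrast** (per unit outcome variance, common factor 2/n omitted):
- difference in change scores: 2(1−r)
- baseline as covariate, or a common baseline mean in both arms: 1−r²
- share recoverable: 1 − (1−r²)/[2(1−r)] = (1−r)/2
- arms compared at week 12 with baseline unused: variance 1, so share recoverable = r²

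**3. With dropout** (50 per arm at baseline, 45 at week 12, monotone, missing at random):
- interaction: 2[(1−r²)/45 + (1−r)²/50]
- common baseline mean: 2(1−r²)/45

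At r = 0.5 these are 0.0433 and 0.0333, a share of 23%. At r = 0.8 they are 0.0176 and 0.0160, a share of 9%. Generalised least squares on the four-visit random-intercept model, with 50, 45, 40 and 36 women per arm, gives the same values.

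| r | 2(1−r) | 1−r² | Recoverable, complete data | Recoverable, planned dropout | r² (week-12 comparison, baseline unused) |
|---|---|---|---|---|---|
| 0.3 | 1.40 | 0.91 | 35% | 33% | 9% |
| 0.5 | 1.00 | 0.75 | 25% | 23% | 25% |
| 0.7 | 0.60 | 0.51 | 15% | 14% | 49% |
| 0.8 | 0.40 | 0.36 | 10% | 9% | 64% |
| 0.9 | 0.20 | 0.19 | 5% | 5% | 81% |

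**4. Equivalence power at 45 per arm**, from the step 1 formula with the SD replaced by the root of each variance. The units of 0.62 are not stated, so both readings are shown.

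| r | Outcome SD = 1: change score → adjusted | 0.62 in SDs of change: change score → adjusted |
|---|---|---|
| 0.3 | 59.9% → 85.0% | 80.5% → 95.5% |
| 0.5 | 80.5% → 92.0% | 80.5% → 92.0% |
| 0.7 | 96.9% → 98.7% | 80.5% → 87.8% |
| 0.8 | 99.7% → 99.9% | 80.5% → 85.4% |

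**5. How far equal SDs can be trusted.** With SDs s₀ and s₁ the share is 1 − s₁²(1−r²)/(s₀² + s₁² − 2r·s₀s₁). In the pilot table (Table 2, MET arm), WMS delayed recall goes from SD 2.39 to 1.17, and the share is 76% at r = 0.5 and 81% at r = 0.8. Rey-O 3-min goes from 5.29 to 6.76, and the share is 10% and 0.1%.

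**6. Illustration from the same table.** Mean WMS delayed recall goes from 5.22 to 6.72 in the yoga arm and from 6.27 to 7.27 in MET. Change scores favour yoga by 1.50 − 1.00 = 0.50. Week-12 means favour MET by 7.27 − 6.72 = 0.55. The adjusted difference (yoga minus MET) is −0.55 + 1.05b for baseline slope b, and changes sign at b = 0.55/1.05 = 0.52. The answer can therefore turn on the slope. This is only an illustration: the population had MCI and included men, and the table does not show how many were tested at week 12.

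**The case against.** The strongest reply is that the planned contrast is valid and that nothing in the plan forbids the adjustment. Both parts stand. A reader might infer that the analysis ignores baseline or is biased. The documents do not support this. A change-score contrast does subtract baseline, with slope 1, and it is unbiased under randomisation. The demographic set is described as only one possibility, so baseline memory is not excluded. What remains is a gap in prespecification and a loss of precision.

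A reader might also quote a fixed loss, such as 10–25%, as a property of this trial. That range needs r between 0.5 and 0.8, equal SDs and complete data. The documents give no r, and the pilot SDs are not equal. Nor do the documents establish that the trial is underpowered. Power below 80% for the change-score contrast requires r below 0.5 and 0.62 read against an outcome SD of 1. The composite is an average of test Z scores and is not said to be re-standardised, so its SD is probably below 1. Assuming three tests with inter-test correlation 0.2 to 0.6, the SD is √[(1+2×0.2)/3] = 0.68 to √[(1+2×0.6)/3] = 0.86. If 0.62 is in Z units, power at r = 0.5 is then already about 93–99% without adjustment.

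Treating baseline as a response is likewise an inference from Hypothesis 1, not a statement in the plan. The conclusion survives either way, because leaving baseline out of the week-12 comparison loses about r² instead.

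Finally, the Data analysis section describes two-sided tests and no equivalence interval, so the power figures above apply to the test in the Power analysis paragraph and not to one that the model section defines. That is a fair limit on the power figures. It does not affect the variance result.

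**Conclusion.** The point holds as an available gain in precision that the plan does not secure. On the likely reading (baseline a response, free group difference), a share (1−r)/2 of the variance of the week-12 contrast is recoverable: 35% at r = 0.3, falling to 5% at r = 0.9. This assumes equal SDs and complete data. With the planned dropout it is about 23% to 9% for r from 0.5 to 0.8. If arms are compared at week 12 without using baseline, the share is about r². The effect on power runs from substantial to almost nil, depending on r and on the units of the margin, and the documents settle neither. The algebra is certain and the size for this trial is not. No bias and no invalid test follow from it.

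**What to change.** For memory and executive function, prespecify before unblinding a longitudinal model that keeps baseline as a response and gives both randomised arms a common baseline mean. This form keeps the within-arm change that Hypothesis 1 needs, and keeps in the analysis women with no post-baseline visit. An unstructured covariance over the four visits would let the data set the baseline slope, whereas random intercepts alone force equal variances.

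For the between-arm contrast only, the alternative is to model post-baseline visits with the baseline domain Z score and its interaction with visit as fixed covariates. This does not estimate change from baseline directly, and it omits women with no later visit, so the two forms are not interchangeable.

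State also which times are responses, the week-12 contrast to be reported, and the units of 0.62. The cost is a changed model statement and, for the covariate form, a few parameters. No extra women, visits or tests are needed. Separately, Table 4 and the neuropsychological testing paragraph do not schedule the battery at week 12, while other text in the same section and the primary outcome require it then. These passages must be reconciled before any week-12 model can be fitted.
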